5.1.6 Study Discharge

Following the successful completion of all procedures at the Week 18 visit, all subjects are to undergo discharge procedures. This will include instructions to the subject to contact the investigational site immediately if any problems or concerns arise during the next 4 weeks of follow-up. Female subjects will complete a pregnancy test. Pregnancy is not to be recorded as an Adverse Event.

5.1.7 Follow-up Period (Week 22)

Subjects will undergo follow-up evaluations 4 weeks after the last dose of study drug. The follow-up can be via phone, providing the patient has no health concerns related to the study. The subject may be asked to return to the investigational site if the Investigator thinks it is advisable for safety reasons. The following assessments will be conducted by phone or other contact at Week 22:

- AE monitoring
- Concomitant medications (query for any possible relationship to an AE)

Following the completion of the follow-up procedures, the subject is officially discharged from the study.

6.0 PROCEDURES FOR HANDLING ADVERSE EVENTS AND SERIOUS ADVERSE EVENTS

6.1 DEFINITION OF AN ADVERSE EVENT

The following definition of adverse event (AE) will be used for this study: Adverse event means any untoward medical occurrence associated with the use of a drug in humans, whether or not considered drug related.

An AE can be any unfavorable and unintended sign (including an abnormal laboratory finding), symptom, or disease (new or exacerbated) temporally associated with the use of the investigational product, regardless of whether it is considered to be related to the investigational product.

The following are examples of AEs:

- Significant or unexpected worsening or exacerbation of the indication under study
- Exacerbation of a chronic or intermittent preexisting condition, including an increase in frequency or intensity of the condition
- New conditions detected or diagnosed after investigational product administration, even if they were present before the start of the study
- Signs, symptoms, or the clinical sequelae of a suspected interaction with another medical product
- Signs, symptoms, or the clinical sequelae of a suspected overdose of either investigational product or a concurrent medication

Overdose should not be reported as an AE or serious adverse event (SAE), but rather the symptoms resulting from the overdose.

Examples of AEs do not include the following:

• Medical or surgical procedures (e.g., endoscopy, appendectomy). The medical condition that led to the procedure as the AE should be reported.

- Situations that are unwanted by the subject but in which an untoward medical occurrence did not occur, for example social inconvenience after admission to a hospital
- Anticipated day-to-day fluctuations of a preexisting disease or condition (present or detected before enrollment) that does not worsen overall
- Expected progression of the disease being studied, including signs or symptoms
 of the disease, unless progression is more severe than expected for the subject's
 condition

AEs may include pre-treatment or post-treatment events that occur as a result of protocol-mandated procedures (e.g., invasive procedures, modification of the subject's previous therapeutic regimen).

AEs should be captured even if they occur during periods without drug treatment, post-treatment periods, known placebo treatment, or in a reference or control group receiving drug or nondrug therapy.

The investigator is responsible for all AE assessments. The investigator and study staff will note all AEs mentioned by the subject at Baseline and during administration of the investigational product. All clinical complaints volunteered by or elicited from the subject during the study will be recorded on the appropriate page of the electronic case report form (eCRF) for the study period indicated. The subject will receive appropriate treatment and medical supervision for any AE that occurs.

All AEs judged to be clinically significant, including clinically significant laboratory abnormalities, will be followed until resolution. All AEs will be summarized in the annual report or more frequently if requested by the regulatory agency. SAEs require special reporting in addition to documentation in the eCRF as described in Section 6.7.

6.2 DEFINITION OF A SERIOUS ADVERSE EVENT

In this study, a serious adverse event is defined as an AE that meets any of the following criteria:

- Results in death
- Is life-threatening. The term life-threatening in the definition of an SAE refers to an event in which the subject was at risk of death at the time of the event. The term life-threatening does not refer to an event that, had it occurred in a more severe form, might have caused death.
- Requires hospitalization or a prolongation of an existing hospitalization. In general, hospitalization signifies that the subject has been detained at the hospital or emergency ward for observation or treatment that would not have been appropriate in the physician's office or out-patient setting. Complications that occur during hospitalization are AEs, but not necessarily SAEs. A medical occurrence or complication that prolongs hospitalization is an SAE. When there is doubt as to whether hospitalization occurred or was necessary, the AE should be considered an SAE. Hospitalization for elective treatments of a preexisting condition that did not worsen from its original Baseline level is not considered an SAE.
- A persistent or significant incapacity or substantial disruption of the ability to conduct normal life functions. This does not include AEs of relatively minor medical significance such as uncomplicated headache, nausea, vomiting, diarrhea, influenza and accidental trauma (e.g., sprained ankle) that may interfere or prevent everyday life functions but do not constitute a substantial disruption.
- A congenital anomaly or birth defect. This refers to the offspring of a study subject.
- An other important medical event. Medical or scientific judgment should be exercised when deciding whether reporting is appropriate for other important medical events that may not result in death, be life-threatening, or require hospitalization but still may jeopardize the subject or may require medical intervention to prevent one of the outcomes listed in this definition. These events should also be considered serious. Examples of such events are intensive treatment in an emergency room or at home for allergic bronchospasm, blood

dyscrasias, or convulsions that do not result in hospitalization or in the development of drug dependency or drug abuse.

An SAE requires additional detailed reports and follow-up. The content of these detailed reports must address the investigator's estimate of causality. The medical monitor will review the SAE to determine if it is an expected SAE (i.e., whether or not the SAE is identified in nature, severity, and frequency in the Investigator's Brochure).

6.3 RECORDING ADVERSE EVENTS AND SERIOUS ADVERSE EVENTS

When an AE or SAE occurs, the investigator is responsible for reviewing all documentation (e.g., hospital progress notes, laboratory, and diagnostic reports) relative to the event(s). The investigator will record all relevant information about any AE (including SAEs) on the AE page of the eCRF. It is not acceptable for the investigator to send photocopies of the subject's medical records in lieu of the properly completed AE or SAE pages of the eCRF. These documents should not be sent unless they are specifically requested by the pharmacovigilance department. If this request occurs, all subject identifiers and protected health information should be blinded on the copies of the medical records before submission to the pharmacovigilance department and to the appropriate authorities.

The investigator will also attempt to report a diagnosis, instead of signs, symptoms, or other clinical information, for the AE. The diagnosis, not the individual signs and symptoms, should be documented on the appropriate page of the eCRF as the AE or SAE. In addition, SAEs need to be reported in the SAE report. AEs being processed as SAEs will also require additional documentation. The study procedures manual provides additional guidelines about reporting SAEs.

6.4 ASSESSMENT OF INTENSITY

The investigator will assess the intensity for each AE and SAE reported during the study on the basis of his or her clinical judgement. The classifications in Table 4 should be used in assigning intensity of each AE recorded in the case report form.

Formatt

Dele

Table 4. Classification of AEs by Intensity^a

Intensity	Definition		
Mild AE (Grade 1)	An event that is easily tolerated by the subject, causing minimal discomfort and not interfering with everyday activities		
Moderate AE (Grade 2)	An event that is sufficiently discomforting to the extent of interfering with normal everyday activities		
Severe AE (Grade 3)	An event that prevents the subject from performing normal everyday activities		
Life-threatening or disabling AE (Grade 4)	An event that, at the time of occurrence, put the subject at risk of death or resulted in a persistent or significantly disability or incapacity		
Death related to AE (Grade 5)	An event that resulted in death		

AE = adverse event

Any AE that changes in intensity or grade during a single occurrence of an AE will be recorded in the eCRF at the highest level experienced by the subject.

An AE that is assessed as severe should not be confused with an SAE. Severity is a category used for rating the intensity of an AE (such as mild, moderate, or severe myocardial infarction). However, AE itself may be of relatively minor medical significance, such as a severe headache. Both AEs and SAEs can be assessed as severe. An AE is considered serious when it meets one of the predefined outcomes described in Section 6.1.

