6.9 LIVER ADVERSE EVENTS

The following algorithm will be used to monitor for drug-induced liver injury (DILI):

If isolated transaminase (AST or ALT) elevations are observed, defined as: Normal bilirubin and absence of clinical hepatitis, AND

- 1. ALT or AST \geq 5 times the ULN if normal at baseline, OR
- 2. ALT or AST \geq 3 times the baseline or \geq 400 U/L if abnormal at baseline

Then

- 1. Repeat liver profile (ALT, AST, bilirubin and PT/INR) within 2 to 3 days, AND
- 2. Monitor the patient with laboratory testing and physical examination 2 to 3 times per week as per the "close observation" definition in the DILI guidance (https://www.fda.gov/downloads/Drugs/.../Guidances/UCM174090.pdf).

If any ONE of the following criteria is met:

- Transaminases (ALT or AST \geq 3 x baseline) AND bilirubin (total bilruibin \geq 2 x ULN), OR
- Cholestatic markers (ALP or GGT > 2 x baseline), OR
- Isolated ALT/AST ≥ 8x ULN or 600 U/L in the presence of normal CPK and LDH and not secondary to cholangitis, OR
- INR increase > 1.5 refractory to vitamin K administration

OR: if any ONE of the following criteria is met for total bilirubin unrelated to hemolysis:

- 1. Doubling of total bilirubin
 - OR: any increase in total bilirubin if there are symptoms of clinical hepatitis (e.g., vomiting, nausea, right upper quadrant pain),
 - OR: there are immunological reactions (rash or >5% eosinophilia),

Then

- 1. study medication must be interrupted, and
- 2. a drug-induced liver injury workup must be initiated for alternate etiologies;
- 3. repeat a liver profile (ALT, AST, total bilirubin, direct bilirubin, ALP) and PT/INR within 48 to 72 hours;
- 4. monitor the patient with further laboratory testing and physical examination 2 to 3 times per week as per the "close observation" definition in the DILI guidance (https://www.fda.gov/downloads/Drugs/.../Guidances/UCM174090.pdf.
- 5. If a subject lives in a remote area, they can be tested locally and the results communicated to the investigator promptly.

Rechallenge

- 1. Only if a firm alternate etiology is identified AND liver tests have returned to baseline (a rechallenge may be considered)
- 2. If cholangitis is the etiology diagnosis must be firmly established according to the protocol definition before a rechallenge is considered

Rechallenge is not recommended if it is determined that the subject has had a drug induced liver injury.

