7.4 PREMATURE STUDY OR SITE TERMINATION

If the sponsor, investigator, medical monitor, study monitor, or appropriate regulatory officials discover conditions arising during the study that indicate that the study should be halted or that the site should be terminated, this action may be taken after appropriate consultation among the sponsor, investigator, medical monitor, and study monitor. The Common Terminology Criteria for Adverse Events (CTCAE) will be used to for the assessment of trial stopping criteria.

The study trial will be stopped if:

- Three patients develop the same Grade 3 CTCAE
- OR: Two patients develop any Grade 4 CTCAE
- OR: One patient develops a Grade 5 CTCAE

Additional conditions that may warrant termination of the study include, but are not limited to, the following:

- The discovery of an unexpected, serious, or unacceptable risk to the subjects enrolled in the study
- A decision on the part of the sponsor to suspend or discontinue testing, evaluation, or development of the product

A study conducted at a single site in a multicenter study may also warrant termination under the following conditions:

- Failure of the investigator to enroll subjects into the study at an acceptable rate
- Failure of the investigator to comply with pertinent regulations of appropriate regulatory authorities
- Submission of knowingly false information from the site to the sponsor, study monitor, or appropriate regulatory authority
- Insufficient adherence to protocol requirements

Study termination and follow-up will comply with the conditions set forth in International Council for Harmonisation E6, Guideline for Good Clinical Practice, Sections 4.12, 4.13, 5.20, and 5.21.

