5.3. SAFETY

5.3.1. Adverse Events

AEs will be mapped to a Medical Dictionary for Regulatory Activities (MedDRA) version 20.1 preferred term (PT) and system organ classification (SOC). If a subject experiences multiple events that map to a single preferred term, the greatest severity grade according to the Common Terminology Criteria for Adverse Events (CTCAE) Version 4.0 will be assigned to the preferred term for the appropriate summaries. Should an event have a missing severity or relationship, it will be classified as having the highest severity and/or assumed related to study medication. The overall occurrence of any TEAEs, TEAE related to study drug, severe TEAEs, serious TEAEs, TEAE leading to discontinuation of study drug, and TEAE leading to death, alongside individual counts of each respective TEAE. The occurrence of TEAEs will be summarized by treatment group by SOC, and PT based on the treatment taken at AE start date. Summaries of the total number of subjects receiving each treatment and the average weeks of exposure for each treatment will be provided for context.

Separate summaries of each TEAE by period, TEAEs leading to the discontinuation of study, TEAEs related to study drug, and serious TEAEs will be generated and summarized by SOC and PT. The occurrence of TEAEs will be summarized by treatment group by SOC, PT, and Severity will also be summarized.

All adverse events reported will be listed for individual subjects showing verbatim term, PT and SOC. All AEs that occurred prior to the initiation of study treatment will be excluded from the tables but will be included in the listings.

Missing onset dates will be imputed as previously outlined in [Section 3.3.5](#) as required to determine treatment-emergent events.

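### Table 4 gives no laboratory basis for Grade 2 or 3, so severity summaries labelled CTCAE can understate asymptomatic laboratory events

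*Protocol*

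**What the plan says.** **Recording.** Protocol 6.1 counts abnormal laboratory findings as AEs. Protocol 5.1.3 to 5.1.5 require clinical deteriorations from Baseline in the central laboratory results to be recorded as AEs.

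**Grading.** Under Protocol 6.4 the investigator grades by clinical judgement, and the Table 4 classifications "should be used in assigning intensity of each AE recorded in the case report form". The first three grades are:
- Grade 1: "An event that is easily tolerated by the subject, causing minimal discomfort and not interfering with everyday activities"
- Grade 2: "An event that is sufficiently discomforting to the extent of interfering with normal everyday activities"
- Grade 3: "An event that prevents the subject from performing normal everyday activities"

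Grade 4 is risk of death, or persistent or significant disability or incapacity. Grade 5 is death. Footnote a attributes the table to CTCAE version 4.0.

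**Action on laboratory values.** Protocol 6.9 lists liver criteria. When any one is met, the first step is "study medication must be interrupted, and" the next is a drug-induced liver injury work-up.

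**Use of the grade.** When several events of one subject map to one preferred term, SAP 5.3.1 states that "the greatest severity grade according to the Common Terminology Criteria for Adverse Events (CTCAE) Version 4.0 will be assigned to the preferred term". It also counts severe TEAEs and tabulates TEAEs by SOC, PT and severity. Protocol 7.4 names CTCAE for its trial stopping criteria, one of which is "Three patients develop the same Grade 3 CTCAE".

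**The concern.** Grades 1 to 3 measure how an event feels and what it stops the subject doing. A raised transaminase or bilirubin without symptoms does neither, so the scale cannot separate a small abnormality from one large enough to interrupt study drug. The SAP then presents severity as a CTCAE v4.0 grade. Because Table 4 is itself footnoted to CTCAE, an investigator has no prompt to look for another scale, and a programmer may take the recorded grade as the CTCAE grade.

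Safety and tolerability are secondary objectives, and 6.9 shows that the protocol takes liver injury seriously. The severity table is where a reader would look for graded hepatic laboratory events by arm, and it may show them as mild.

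**Working it through.** There is no stated figure to reproduce and no calculation of power or error rate applies. The check applies the Table 4 wording to each interruption criterion in Protocol 6.9, then asks what else in the SAP would show such an event.

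**Step 1. Grade of an asymptomatic case.** Protocol 6.9 has four criteria in its first list and three for bilirubin: 4 + 3 = 7.

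| Interruption criterion in 6.9 | Can be met without symptoms? | Grade by Table 4 if asymptomatic |
|---|---|---|
| ALT or AST ≥ 3 x baseline with total bilirubin ≥ 2 x ULN | Yes | 1, or 4 if at risk of death |
| ALP or GGT > 2 x baseline | Yes | 1, or 4 |
| Isolated ALT/AST ≥ 8 x ULN or 600 U/L, with normal CPK and LDH and no cholangitis | Yes | 1, or 4 |
| INR increase > 1.5 refractory to vitamin K | Yes | 1, or 4 |
| Doubling of total bilirubin, not from hemolysis | Yes | 1, or 4 |
| Bilirubin rise with symptoms of clinical hepatitis | No | Depends on symptoms |
| Immunological reaction (rash or > 5% eosinophilia) | Yes, through eosinophilia | 1, or 4 |

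Six of seven can be met on laboratory results alone. On the table's wording none of the six reaches Grade 2 or 3 in an asymptomatic subject.

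**Step 2. Which scale governs.** Protocol 6.4 fixes Table 4 for the case report form. Protocol 7.4 and SAP 5.3.1 name CTCAE. No section says that laboratory AEs are regraded from measured values, or which scale prevails if the two differ.

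**Step 3. What the other displays show.**
- *Shift tables (SAP 5.3.2)* use low, normal and high. Entry requires ALP ≥ 1.5 x ULN. Doubling from there gives 2 x 1.5 = 3 x ULN or more, which is high to high. AST and ALT may be up to 5 x ULN at entry, so a subject who enters above ULN and reaches 8 x ULN is also high to high. A bilirubin baseline below 0.5 x ULN doubles to below 2 x 0.5 = 1 x ULN, which is normal to normal. The tables cover Periods 1 and 2 only, at the end of each period.
- *Descriptive summaries (SAP 5.3.2)* give means and extremes, not the number of subjects beyond a 6.9 threshold.
- *ALP and GGT models and subject-level ALP plots (SAP 5.2.2, 5.2.5)* show these two markers well, but give no threshold counts and do not cover ALT, AST or INR.
- *Listings* hold every value without summarising it.
- *TEAEs leading to discontinuation (SAP 5.3.1)* need not include a 6.9 interruption, because 6.9 allows rechallenge to be considered. The SAP specifies no count of interruptions.

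**Step 4. A side effect.** SAP 5.3.1 gives an event with missing severity the highest severity. An ungraded laboratory event would thus rank above a documented, asymptomatic ALT of 8 x ULN graded mild.

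**The case against.** The strongest reply is that the CTCAE is named three times: in the footnote to Table 4, in Protocol 7.4 and in SAP 5.3.1. The SAP does not say that the CTCAE grade is copied from Table 4, and Protocol 7.4 does not cite Table 4. Subject protection does not depend on the severity table either, since 6.9 acts on numeric values, a safety endpoint in Protocol 3.3.2 includes clinically significant laboratory abnormalities whatever their grade, and a DSMB oversees safety.

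Much of this stands, and it rules out three stronger readings that a reader might infer:
- *Every asymptomatic laboratory AE must be Grade 1.* Not so. Grade 4 rests on risk of death or on disability, and 6.4 allows clinical judgement.
- *The trial cannot show a liver signal.* Not so. ALP is the primary endpoint and is plotted by subject, GGT has its own model, bilirubin and other laboratory results are summarised and listed, and symptomatic liver events can be graded higher.
- *Such events can never count toward Protocol 7.4.* The documents do not settle this, because they do not say whether 7.4 draws on the recorded Table 4 grade.

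It is also fair that grades based on ULN could attach to disease present at entry, and that fixing which grade counts in 7.4 would amount to setting a stopping rule.

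The reply does not supply the missing link. The only grading instruction given to investigators is Table 4, and naming CTCAE downstream does not turn an activity scale into a laboratory one.

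**Conclusion.** The point holds as an unreconciled grading scale. Following 6.4 as written puts asymptomatic laboratory AEs at Grade 1 unless they are judged to put the subject at risk of death. SAP 5.3.1 then labels severity as CTCAE v4.0 without saying how the recorded grade becomes that grade. The severe-TEAE count and the SOC/PT/severity table can understate laboratory events, and the remaining displays offset this only in part.

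Size: six of the seven interruption criteria in 6.9 can be met without symptoms and so are exposed to this. The number of subjects affected cannot be estimated, because the documents give neither event rates nor the CTCAE laboratory limits. An event whose CTCAE grade would be 1 anyway is not misgraded.

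Assumptions: investigators apply Table 4 literally; the SAP severity comes from the recorded grade; and CTCAE v4.0 grades laboratory results by numeric limits, which the documents name but do not reproduce. The primary analysis is unaffected. This should be corrected before database lock.

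**What to change.** 1. **Protocol 6.4:** limit Table 4 to clinical events. SAP 1.1 records that enrollment has stopped, so this helps only events still to be graded, and the SAP changes carry most of the benefit.
2. **SAP 5.3:** derive laboratory severity by program from the collected values using CTCAE v4.0, the standard the SAP already names. Show it against the baseline grade, because subjects enter with raised ALP and possibly raised ALT or AST.
3. **SAP 5.3:** add a count, by treatment, of subjects who meet each numeric threshold listed in Protocol 6.9, in all three periods. This needs no outside limits. CPK and LDH are not named in the schedule of events, so count the ALT/AST threshold on its numeric part and footnote the qualifiers.
4. **Reconciliation:** Protocol 6.4, 6.9 and 7.4 and SAP 5.3.1 must be reconciled on which grade is meant. The content of the stopping rule is for the sponsor and is not proposed here.

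Cost: revised text in 6.4 and the SAP, and a little more programming on data already scheduled. More higher-grade laboratory events may be displayed; showing the baseline grade beside them lets a reader separate new abnormalities from disease present at entry.
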